4.1.3.1. Relapse under Conservative Definition (SVR)

Relapse date is defined as the first visit after the appropriate window end date where observed data for either HBsAg or HBV DNA is greater than the lower limit of quantification (LLOQ) or the use of rescue medication.

4.1.3.2. Relapse under the Modified Definition of SVR

Relapse date is defined as the first visit after the appropriate window end date where observed data for either HBsAg or HBV DNA is $>$ LLOQ at two consecutive visits for the same parameter or the use of rescue medication.

Any observation of HBsAg \geq LLOQ or HBV DNA \geq LLOQ at a visit must be confirmed individually at a consecutive visit (including unscheduled visits or the first visit after the end of the analysis window).

4.2. Primary Endpoint Analyses

HBsAg and HBV DNA assessments from the end of treatment analysis window (Week 48 or Week 36 for Arm 1 and Arm 2 respectively) to the off-treatment Week 24 analysis window will be used to analyse the primary endpoint for each arm. The primary analysis for the primary endpoint will be conducted once the database lock has been achieved and the last participant has completed the Week 72 visit.

The primary efficacy endpoint is achieving a sustained virologic response for 24 weeks after the planned end of GSK3228836 and PegIFN sequential treatment in the absence of rescue medication. Sustained virologic response (SVR) is defined as observing HBsAg <LLOQ and HBV DNA <LLOQ at each analysis window in the 24 weeks after the end of sequential treatment. Analysis windows for the post GSK3228836 treatment assessments are defined in Section 4.2.2.1.

An estimation approach with no hypothesis testing will be used to address the primary objective. The primary assessments of interest are the point estimate of SVR rate and 95% credible intervals. In addition, posterior probabilities that the true SVR rate in each treatment arm is greater than a range of clinically meaningful response rates will be provided. The point estimates for SVR will be calculated using a Bayesian probability approach. Comparisons between treatment arms as defined in the key secondary/exploratory objectives will be assessed using probability inference approaches.

4.2.1. Definition of Estimands

The primary estimand supporting the primary objective is defined as:

- **Population:** Participants with CHB on stable NA therapy.
- **Treatment:** 300 mg GSK3228836 for 12 or 24 weeks followed by up to 24 weeks of PegIFN therapy while on stable NA therapy.
- **Variable (Categorical):** Participants achieving sustained virologic response (SVR) (HBsAg <LLOQ and HBV DNA <LLOQ) for 24 weeks after the planned end of sequential treatment, without the use of rescue medication.
- **Intercurrent Events:**
 - For discontinuation of, interruption in, or non-adherence to GSK3228836 or PegIFN unrelated to any wide disruptive events (such as COVID-19 pandemic), the data will be analysed as collected (treatment policy strategy).
 - For participants that are ineligible to receive PegIFN, the data will be analysed as collected (treatment policy strategy).
 - Use of rescue medication will be incorporated in the definition of the endpoint (composite strategy).
 - For wide disruptive events (such as COVID-19 pandemic) leading to discontinuation of, significant interruption in, or non-adherence to GSK3228836 and PegIFN, data collected after the intercurrent event will

be set to missing and the response will be imputed assuming missing at random in the Bayesian model. Additional details provided in Section 4.2.2.2 (hypothetical strategy).

- **Population Summary:** The percentage of participants in each treatment group who achieve sustained virologic response (SVR) (HBsAg <LLOQ and HBV DNA <LLOQ) for 24 weeks after the planned end of sequential treatment without rescue medication usage.

4.2.2. Main Analytical Approach

A Bayesian model will be fitted using Markov Chain Monte Carlo (MCMC) methods, and will be used to estimate the posterior probability of SVR sustained virologic response for each arm incorporating the baseline analysis stratification factors (Table 1) [Jones, 2011].

The model below differs from the Bayesian hierarchical model specified in the 209348 Protocol Amendment v.1.0 (24-Sep-2021). This hierarchical model included a random effect ψ_g for each strata, an interaction term for treatment by stratum, and was applied separately for each arm. However, when the model was run on data from the administrative interim analyses (AIAs) (see Section 4.7), there were stratum with zero counts which caused perfect prediction of the response variable for some values of the predictors (quasi-complete separation). To address this issue, the hierarchical model was simplified to the Bayesian logistic regression model below, with only fixed effects and combined data across arms.

The number of responders is assumed to follow a binomial distribution:

$$\text{Number of responders } r_g \sim \text{Binomial}(n_g, p_g), \quad g = 1, 2, 3, 4$$

where we define r_g as the number of SVR responders among n_g participants, p_g as SVR rate $\frac{r_g}{n_g}$, and index g refers to the stratum number as defined in Table 1 below.

The analysis model is defined as:

$$\theta_g = \text{logit}(P_g) = \log\left(\frac{P_g}{1-P_g}\right) = \tau + \gamma_1 I_{\{B1+\}} + \gamma_2 I_{\{B2+\}} + \gamma_3 I_{\{\text{Arm}\}}$$

where τ, γ_1, γ_2 , are all parameters. Thus,

$$\theta_1 = \tau$$

$$\theta_2 = \tau + \gamma_1$$

$$\theta_3 = \tau + \gamma_2$$

$$\theta_4 = \tau + \gamma_1 + \gamma_2$$

Priors:

$$\tau \sim \text{Normal}(0, 10^6)$$

$$\gamma_k \sim \text{Normal}(0, 10^6), k = 1, 2$$

Table 1 Baseline Analysis Strata

Stratum	B ₁ : HBsAg	B ₂ : HBeAg
1: HBsAg ≤3 log IU/mL and Negative HBeAg	B ₁ (≤3 log IU/mL)	B ₂ (Negative)
2: HBsAg >3 log IU/mL and Negative HBeAg	B ₁₊ (>3 log IU/mL)	B ₂ (Negative)
3: HBsAg ≤3 log IU/mL and Positive HBeAg	B ₁ (≤3 log IU/mL)	B ₂₊ (Positive)
4: HBsAg >3 log IU/mL and Positive HBeAg	B ₁₊ (>3 log IU/mL)	B ₂₊ (Positive)

The point estimates and 95% credible intervals of sustained virologic response rate in each of the treatment arms will be calculated.

For each arm, the posterior distribution of SVR rate $P(p_g|data)$, $g=1,2,3,4$ will be derived for each analysis stratum using the model specified above:

$$P(p_1|data) = P\left(\frac{e^{\theta_1}}{1 + e^{\theta_1}} | data\right)$$

$$P(p_2|data) = P\left(\frac{e^{\theta_2}}{1 + e^{\theta_2}} | data\right)$$

$$P(p_3|data) = P\left(\frac{e^{\theta_3}}{1 + e^{\theta_3}} | data\right)$$

$$P(p_4|data) = P\left(\frac{e^{\theta_4}}{1 + e^{\theta_4}} | data\right)$$

The posterior distribution of the arm-level SVR rate will be derived using a mixture of the posterior distributions of SVR rate for each analysis stratum in that arm. The weights are proportional to the sample size of each analysis stratum in each arm:

$$P(p|data) = \sum_{g=1}^4 w_g P(p_g|data), \text{ where } w_g = \frac{n_g}{\sum_{g=1}^4 n_g}$$

Posterior probabilities of SVR rates exceeding a range of clinically meaningful response rates, e.g., 30%, 35%, 40%, will be generated using the approach specified above for each arm. If monotherapy in study 209668 (B-Clear) is deemed successful, then posterior probabilities will be derived for a difference > 10% and <15% of the SVR rates between any B-Together arm and the B-Clear chosen arm to evaluate whether sequential therapy is successful.

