4.2.3. Sensitivity Analyses

For the primary estimand, a sensitivity analysis will be performed using the Bayesian model described in Section 4.2.2. The final inference from the Bayesian model will account for the missing data assuming MAR, regardless of the reason for missingness.

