 - For wide disruptive events (such as COVID-19 pandemic) leading to discontinuation of, significant interruption in, or non-adherence to GSK3228836 or PegIFN, data collected after the intercurrent event will be set to missing and the response will be imputed using all available data for participants for whom SVR can be assessed. (hypothetical strategy).

Population Summary: Difference in percentage of participants who achieve SVR for 24 weeks after the planned end of sequential treatment between treatment arms

Categorical Variables

The following categorical variables are defined for this objective:

- Achieving SVR (HBsAg <LLOQ and HBV DNA <LLOQ) at the planned end of sequential treatment and over the 24 weeks follow-up for each treatment arm.

Main Analytical Approach

The secondary efficacy comparison of interest is the difference in sustained virologic response rate for 24 weeks after the planned end of sequential treatment between treatment arms:

- Arm 1 vs. Arm 2 in percentage of participants achieving SVR for 24 weeks after the planned end of sequential treatment, without use of any rescue medication.

Comparison between treatment arms will be made by calculating the difference between the posterior distributions of the response rate in each arm which will be summarised to obtain posterior means and CIs. Samples from the posterior distribution of the response rates in each arm will also be used to obtain posterior probabilities of interest. The point estimates of differences in SVR rate with 95% credible intervals will be calculated for the treatment comparisons described in the estimands. Posterior probabilities $\Pr(\text{Arm 1} - \text{Arm 2} > 0)$ and $\Pr(\text{Arm 2} - \text{Arm 1} > -0.05)$ will be presented to aid selection of treatment regimen.

Model Checking and Diagnostics – MCMC Mixing Diagnosis

The same approach in model checking and diagnostics will be applied as for the primary analysis (Section 4.2.2.3).

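### The pooled primary model in SAP 4.2.2 has an arm term in its logit line but not in its likelihood index, stratum predictors or priors; programmed as printed, both arms get the same stratum SVR rates

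*SAP*

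**What the plan says.** The version history for SAP v4.0 and the text of Section 4.2.2 agree that the per-arm hierarchical model was dropped: "the hierarchical model was simplified to the Bayesian logistic regression model below, with only fixed effects and combined data across arms". The specification that follows has these parts:

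- **Likelihood:** r_g ~ Binomial(n_g, p_g) for g = 1 to 4, where the index "refers to the stratum number as defined in Table 1 below". There is no arm index.
- **Logit line:** θ_g = τ + γ₁·I(B1+) + γ₂·I(B2+) + γ₃·I(Arm).
- **Expanded predictors:** θ₁ = τ; θ₂ = τ + γ₁; θ₃ = τ + γ₂; θ₄ = τ + γ₁ + γ₂.
- **Priors:** Normal(0, 10⁶) for τ and for γₖ, k = 1, 2.
- **Stratum rates:** p_g = exp(θ_g)/(1 + exp(θ_g)), introduced by "For each arm, the posterior distribution of SVR rate".
- **Arm-level rate:** "derived using a mixture of the posterior distributions of SVR rate for each analysis stratum in that arm", with weights given by that arm's stratum sizes.

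Several results rest on this model:

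- the probabilities of exceeding 30%, 35% and 40%;
- a conditional comparison "between any B-Together arm and the B-Clear chosen arm to evaluate whether sequential therapy is successful";
- SAP 4.2.3, where "a sensitivity analysis will be performed using the Bayesian model described in Section 4.2.2";
- SAP 4.3.1.3, which compares the arms by "calculating the difference between the posterior distributions of the response rate in each arm" and reports two posterior probabilities that "will be presented to aid selection of treatment regimen".

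**The concern.** In a pooled model the arm coefficient is the only thing that lets the arms differ within a stratum. The SAP writes it once and then leaves it out of every line a programmer would use to compute an arm's rate. No other section repairs this: neither the version history, nor 4.3.1.3, nor 4.6.1, nor the table of changes in 4.8 gives γ₃ a prior, defines I(Arm), or prints the second arm's four predictors.

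The omitted lines fit the protocol's model. In Protocol 9.4.2.4, k = 1, 2 meant the two stratification factors, and in 9.4.3.3 the log odds were estimated separately by arm. Carry-over from that model is a likely explanation, though only an inference.

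At stake are the primary SVR estimate of at least one arm, its threshold probabilities, and the comparison between 24 and 12 weeks of GSK3228836 that is meant to inform the choice of regimen.

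**Working it through.** **The plan's own figures.** Section 4.2.2 states no numerical result. The nearest are the operating characteristics in SAP Section 5, from an unstratified per-arm Beta(0.5, 0.5) calculation. At n = 50 they reproduce: 12 or more responders has probability 86.1% at a true rate of 30% (stated ~86%), and 17 or more has 84.4% at a true rate of 40% (stated 84%). They do not use the 4.2.2 model and are unaffected.

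**Algebra.** Let w_{g,a} be the share of arm a in stratum g. With the printed θ, p_g does not depend on the arm, so

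rate(Arm 1) − rate(Arm 2) = Σ_g (w_{g,1} − w_{g,2})·p_g.

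If the stratum mix is the same, this is zero whatever the responder counts. If the mix differs, it measures case mix only.

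**Illustration.** The documents give no counts by stratum, so these are assumed:

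- *Equal mix:* 12/24/4/10 participants in strata 1 to 4 of each arm; responders 7/8/1/1 (17 of 50) and 4/4/1/1 (10 of 50).
- *Unequal mix:* 15/21/4/10 and 10/26/4/10; responders 8/7/1/1 (17) and 4/4/1/1 (10).

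The posterior was sampled with two chains, 5,000 burn-in and 200,000 kept draws each. Normal(0, 10⁶) was read as a variance, and the same prior was given to γ₃. The arm rate is Σ w_g·p_g per draw. The printed θ can be used in three ways: fit γ₃ and then drop it with Arm 2 as reference, the same with Arm 1 as reference, or fit four cells with no arm index.

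Equal mix:

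| Reading | Arm 1 | Arm 2 | Difference (points) | Pr(rate > 30%), Arm 1 / Arm 2 | Pr(Arm 2 − Arm 1 > −0.05) |
|---|---|---|---|---|---|
| γ₃ carried through | 34.0% | 20.0% | 14.0 (about −2 to 30) | 0.73 / 0.04 | 0.14 |
| Printed θ, Arm 2 reference | 20.0% | 20.0% | 0 | 0.04 / 0.04 | 1.00 |
| Printed θ, Arm 1 reference | 34.0% | 34.0% | 0 | 0.73 / 0.73 | 1.00 |
| Printed θ, no arm index | 27.0% | 27.0% | 0 | 0.23 / 0.23 | 1.00 |

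With γ₃ carried through, Pr(Arm 1 − Arm 2 > 0) is about 0.95; with the printed θ the difference is exactly zero in every draw.

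Unequal mix: the weights are 0.30/0.42/0.08/0.20 and 0.20/0.52/0.08/0.20, so the difference under the printed θ reduces to 0.10·(p₁ − p₂). The 14.0-point mean difference shrinks to 2.1, 2.5 or 2.5 points for the three readings in the order of the table. In the no-arm fit Pr(Arm 1 − Arm 2 > 0) is 0.99, a near-certainty that comes from case mix alone.

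**Mixture as printed.** Section 4.2.2 describes a mixture of stratum posteriors rather than a weighted average. The means are the same under either. Intervals are wider: with equal mix and γ₃ carried through, the difference is 14.0 (−28.6 to 57.6) and Pr(Arm 2 − Arm 1 > −0.05) is 0.32. With the printed θ the mean difference is 0 and that probability is 0.69 to 0.71. The omission matters under both formulas.

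**The case against.** The strongest reply is that intent is plain. The equation that defines the model contains the arm term, and the four printed predictors are exactly that equation with I(Arm) = 0. They are a correct expansion for the reference arm, and only the second set is missing. The text asks repeatedly for rates by arm, so equal rates would need a programmer to ignore the defining equation or to fit γ₃ and discard it. The error would also be visible: SAP 4.3.1.1 requires observed response percentages by arm, overall and by stratum, and 4.6.1 requires responder counts by arm. The planned interim analysis uses a separate per-arm Beta-Binomial calculation, and the study is descriptive.

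Most of this is fair, and it limits the finding to a contradiction rather than an instruction to produce equal rates. It does not remove it. A programmer who follows the logit line must still supply a prior and a coding that the SAP does not state, and in a Bayesian analysis the prior is part of the specification. Detection is likely when identical estimates sit beside 17 and 10 responders, but less so with unequal mix, where the output shows a small difference with high posterior probability.

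Symbols may have been lost in converting the PDF. Table 1 in this section lacks the minus signs that the protocol's matching table has, and the list of parameters ends in a stray comma, so that list is not relied on. Even if the prior line were also doubted, a lost symbol would not explain four complete predictors without γ₃ and a likelihood indexed by stratum only.

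**Conclusion.** The concern holds. The primary model in SAP 4.2.2 is internally inconsistent and incomplete: γ₃·I(Arm) is in the logit line, but the likelihood index, the predictors that produce the rates and the priors do not carry it. If the printed predictors are followed, the within-stratum arm effect disappears from the primary estimates, the threshold probabilities, the conditional B-Clear comparison, the sensitivity analysis and the Arm 1 versus Arm 2 comparison. That consequence is algebraic. Its size in the illustration, a 14.0-point difference reduced to zero or to 2.1 to 2.5 points, rests entirely on assumed counts and is not an estimate of an error in this trial. The documents do not show what was programmed. Because this is the primary model and the correction is small, it should be made.

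**What to change.** Write the model by stratum g and arm a:

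- r_{g,a} ~ Binomial(n_{g,a}, p_{g,a}), g = 1 to 4, a = 1, 2;
- θ_{g,a} = logit(p_{g,a}) = τ + γ₁·I(B1+) + γ₂·I(B2+) + γ₃·I(Arm), stating which arm is coded 1;
- list γ₃ as a parameter and extend the stated prior to k = 1, 2, 3;
- use p_{g,a} and w_{g,a} = n_{g,a}/Σ_g n_{g,a} in the arm-level rates, the threshold probabilities and the difference in 4.3.1.3.

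Confirm that the analysis program carries γ₃ into each arm's rates. The correction is the same whether the arm-level rate is the printed mixture or a weighted average.

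The cost is a few lines of text and one prior index, with no new data and no change to the model in the logit line. The prior on γ₃ is a natural extension but is not stated now. SAP v4.0 is dated 22 March 2023, and SAP Table 8 projected primary-endpoint data on 100 participants by the January 2023 review. The edit should therefore be logged and dated as a clarification.

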SAP v.4.0	22 Mar 2023	209348 Amd v.1.0 (24-Sep-2021)	Section 4.1.3 Added Relapse Definitions	Additional outputs for EoS include relapse rates on GSK3228836, PegIFN, and OT. Relapse is also defined differently for the conservative and modified definitions of SVR.

SAP Version	Approval Date	Protocol Version (Date) on which SAP is Based	Change	Rationale
			
Section 4.2.2 Model simplification by combining data across both treatment arms and removal of random effect from Bayesian model
	
Addresses the quasi-complete separation of the response variable when the model is run separately for each treatment arm (original model). In addition, the parameter estimates for the original hierarchical model do not converge, and the hierarchical model diagnostics are poor.

			
Section 4.2.2.1 Definition of worst case selection within analysis windows
	
Alignment with conservative and modified definitions of SVR

			
Section 4.2.2.2 Combined Sections for Handling Missing Data On-treatment, End of Treatment,
	
Maintain consistency with handling intercurrent events and missing data throughout the study

SAP Version	Approval Date	Protocol Version (Date) on which SAP is Based	Change	Rationale
			and Post-treatment	
			Section 4.3.1.1 Added Time from Bepi EOT to Relapse by HBsAg Categories Endpoint	Added Time to Event endpoint analysed during administrative IAs (AIAs)
			Section 4.4.1 Moved Exploratory Efficacy Endpoints to main body of SAP with reference in the IA section	Provide clarify that exploratory endpoints will be produced for both the planned IA and for EoS
			Section 4.5.3.1 Added information on handling duplicate LAB values at the same date/ timepoint	Clarity for programming purposes

SAP Version	Approval Date	Protocol Version (Date) on which SAP is Based	Change	Rationale
			Section 6.1.5 Update to study intervention compliance and study dose compliance calculations	Adjust for PegIFN treatment period

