4.2.2.3. Model Checking and Diagnostics – MCMC Mixing Diagnosis

Two sampling chains will be run, with differing starting values and each with a burn-in period of 5,000 samples, to ensure adequate sampling from the posterior. The starting values will be as described above in Section 4.2.2.

Mixing will be regarded as “each chain is independently realizing values similar to those for which the other chains have also sampled.” Adequate mixing will be concluded if the chains meet following conditions:

1. The Brooks-Gelman Ratio (BGR) (Brooks, 1998) for each parameter is in the interval (0.8, 1.2).
2. Each chain appears mix well, upon visual inspection of each chain's trace plot, including assessing the mutual overlap of the chains for each parameter.
3. Each kernel density plot appears smooth upon visual inspection.

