4.6. Other Analyses

4.6.1. Subgroup Analyses

Descriptive summaries by subgroups defined in Table 7 will be provided. Number of responders, posterior mean and 95% equal-tail credible interval of the SVR response rate will be reported by subgroups as defined in the model specification section for each treatment arm. The corresponding posterior probability of SVR rate exceeding a range of clinically meaningful response rates will also be reported by subgroups as defined in the model specification section for each treatment arm. No statistical comparison between subgroups will be performed.

If the number of participants is too small (<5 per subgroup category) within a subgroup, then the subgroup categories may be redefined prior to unblinding the study. If the category cannot be refined further, then descriptive rather than statistical summaries may be presented for the specific subgroup.

Table 7 Subgroups and Subgroup Categories

Subgroup	Categories
HBeAg Status	Positive (\geq 0.09 U/mL); Negative (<0.09 U/mL)
Baseline HBsAg	Low (\leq 3 log ₁₀ IU/mL); High (>3log ₁₀ IU/mL) <=3, >3-3.5, >3.5-4 and >4
Age group	EMA: <18; \geq 18-64; \geq 65 – 84, \geq 85: FDA: \leq 18; \geq 19-64; \geq 65 Clinical and Epi (Group 1): <50; \geq 50
Sex	Male; Female
Race	American Indian or Alaska Native; Asian; Black or African American; Native Hawaiian or Other Pacific Islander; White
Baseline viral genotype	A; B; C; D; Other; Unknown
Baseline BMI	<30; \geq 30
Baseline ALT	\leq ULN; >ULN; \leq ULN, > ULN to \leq 2x ULN, > 2x ULN to \leq 3x ULN, > 3x ULN to \leq 5x ULN, > 5x ULN to \leq 10x ULN, >10x
Baseline METAVIR Fibrosis Score	If enough data are available (\geq 5 participants per group per arm): F0 – F2; F3
Time on current NUC	< 3 years; \geq 3 years
Type of current NUC	TAF/TDF; Entecavir; Other

Subgroup	Categories
Duration of Hep B Infection	<5 years; ≥ 5 years - <10 years; ≥ 10 years - <20 years; ≥ 20 years
Baseline mutations in the binding site	Present; Absent

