5. SAMPLE SIZE DETERMINATION

For the entire study, approximately 100 participants will be enrolled and randomised to achieve approximately 50 participants in each treatment group:

- 24 weeks treatment of GSK3228836 followed by up to 24 weeks treatment of PegIFN
- 12 weeks treatment of GSK3228836 followed by up to 24 weeks treatment of PegIFN

It is assumed that the number of responders follows a Binomial distribution, with a weakly informative prior (Beta (0.5, 0.5)) for the true RR. The precision for a range of RRs with 95% credible intervals are shown in [Table 11](#).

Table 11 95% Credible Interval of Response Rate

Number of Responders	Response Rate	95% Credible Interval*
9	18%	9% - 30%
10	20%	11% - 33%
11	22%	12% - 35%
12	24%	14% - 37%
13	26%	15% - 39%
14	28%	17% - 41%
15	30%	19% - 44%
16	32%	20% - 46%
17	34%	22% - 48%
18	36%	24% - 50%
19	38%	26% - 52%
20	40%	27% - 54%

*95% equal-tailed interval

The historical RR of a combination therapy of NA and PegIFN was 10% with 48 week's treatment [[Ren, 2019](#); [Lee, 2018](#)]. The lower bounds of 95% credible intervals will exclude the RR of 10% if observed RR is greater than or equal to 20% (10 responders out of 50 participants) in an arm.

The posterior probabilities that the true sustained virologic RR is greater than a range of RRs will be calculated from the implied Beta posterior, given the actual number of responders observed.

The operating characteristics based on at least 65% posterior confidence that the true rate exceeds a threshold of interest, are shown in [Table 12](#) for various sample sizes and true

cure rates. The operating characteristics shown are based on a Bayesian inference without consideration of baseline stratification factors.

Table 12 End of study (EoT+24wks) Operating Characteristics by Sample Size

Criterion	Sample Size per Arm	Minimum Number (%) or Responders Required to Meet Criterion	Probability of Meeting Criterion under Various Assumptions			
			True SVR rate = 20%	True SVR rate = 30%	True SVR rate = 35%	True SVR rate = 40%
Probability (true response rate > 20%) > 65%	30	7 (23%)	39%	84%	94%	98%
	40	9 (23%)	41%	89%	97%	99%
	50	12 (24%)	29%	86%	97%	99%
	60	14 (23%)	31%	90%	98%	100%
Probability (true response rate > 30%) > 65%	30	10 (33%)	6%	41%	64%	82%
	40	14 (35%)	2%	30%	56%	79%
	50	17 (34%)	1%	32%	61%	84%
	60	20 (33%)	1%	33%	65%	88%
Probability (true response rate > 40%) > 65%	30	14 (47%)	0%	4%	12%	29%
	40	18 (45%)	0%	3%	12%	31%
	50	22 (44%)	0%	3%	12%	33%

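### SAP 4.2.2 keeps Normal(0, 10^6) log-odds priors, so a factor level with no responders in either arm would be reported with an SVR credible interval of about 0% to 0%

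*SAP*

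**What the plan says.** Protocol 9.4.2.4 planned a hierarchical logistic model. It put Normal(0, 10^6) priors on the intercept and the two factor effects, and a random stratum effect distributed Normal(0, ω²) with ω ~ Half-Normal(1). That random effect was the only term with any shrinkage.

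SAP 4.2.2 explains why this model was abandoned. In the administrative interim data, "there were stratum with zero counts which caused perfect prediction of the response variable for some values of the predictors (quasi-complete separation"). The remedy is stated in the next sentence: "the hierarchical model was simplified to the Bayesian logistic regression model below, with only fixed effects and combined data across arms". The v4.0 entry in the SAP version history describes the gain as removing the separation seen when each arm is modelled on its own.

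The intercept τ and the factor effects γ1 (HBsAg) and γ2 (HBeAg) keep Normal(0, 10^6). The new arm effect γ3 appears in the model equation, but the prior line covers k = 1, 2 only, so γ3 has none.

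The model feeds two kinds of output. SAP 4.2.2 derives an SVR posterior for each stratum within each arm and combines these with sample-size weights into the arm-level rate. SAP 4.6.1 says that the "posterior mean and 95% equal-tail credible interval of the SVR response rate will be reported by subgroups", with threshold probabilities alongside. SAP 4.2.2.3 asks for a Brooks-Gelman ratio (BGR) between 0.8 and 1.2 and for visual checks of trace and density plots. It does not say what to do if they fail. No section gives a fallback for a factor level still without responders after pooling.

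The sample-size section (SAP 5) uses a different model, "with a weakly informative prior (Beta (0.5, 0.5)) for the true RR".

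**The concern.** Separation arises from the pattern of zero counts. Pooling arms removes it only if the other arm supplies at least one responder at the affected factor level. If neither arm does, the main-effects model is still separated. The prior alone then fixes how far below zero the coefficient goes, and an SD of 1000 on the log-odds scale sends it far enough that the fitted response rate is zero to any printable precision.

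At stake is the reading of the stratum and subgroup tables. Seeing no responders among, say, 28 HBeAg-positive participants is compatible with a true SVR of several percent. A 0% to 0% interval would instead state that response at that level is impossible, and every posterior probability of exceeding a threshold would follow suit.

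**Working it through.** **1. The plan's own figures.** With r responders of n, the SAP 5 posterior is Beta(r + 0.5, n − r + 0.5). For 10/50, Beta(10.5, 40.5) gives 10.8% to 32.6%, against the stated 11% to 33%. At n = 50 the rules reproduce: 12 responders for the 20% threshold, met with probability 86% if the true rate is 30%; 17 for the 30% threshold, met with probability 84% if the true rate is 40%. The documents give no interval for an empty factor level.

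**2. What the prior implies.** The model is logit(p) = τ + γ1·[HBsAg >3 log] + γ2·[HBeAg-positive] + γ3·[Arm]. I read 10^6 as a variance (SD 1000), because protocol 9.4.2.4 writes its random effect as Normal(0, ω²). For the reference stratum, where SAP 4.2.2 sets θ1 = τ, the prior probability that p lies between 1% and 99% is 2Φ(ln 99/1000) − 1 = 2Φ(0.004595) − 1 = 0.0037. The other 99.6% sits beyond those limits.

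**3. Posterior for an empty level.** If no HBeAg-positive participant responds in either arm, their likelihood contribution is a product of (1 − p)^n terms. It rises towards 1 as γ2 goes to minus infinity, so the posterior of γ2 is close to the negative half of Normal(0, 1000²). Its 97.5th percentile is −1000 × Φ⁻¹(0.5125) = −31.3. The odds are therefore multiplied by about e^−31.3 ≈ 2.5 × 10⁻¹⁴ even at the upper limit. Reading 10^6 as an SD only makes this more extreme.

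**4. Numerical fits.** The documents give no stratum sizes or responder counts, so all stratum data are assumed; γ3 is given the same prior as the other parameters, also an assumption. The 0/14 case has 50 per arm, with 10 and 7 responders among the HBeAg-negative. The 0/15 case has HBeAg-negative responders of 6/16 (HBsAg ≤3 log) and 4/19 (>3 log) in Arm 1, and 5/16 and 3/19 in Arm 2.

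| HBeAg-positive responders | Prior SD | Arm 1, 95% interval | Arm 2, 95% interval |
|---|---|---|---|
| 0/14 and 0/14 | 1000 | 0.00% to 0.00% | 0.00% to 0.00% |
| 0/14 and 0/14 | 2.5 | upper limit about 10% | upper limit about 7% |
| 0/15 and 0/15 | 1000 | 0% to 0% | 0% to 0% |
| 0/15 and 0/15 | 10 | 0.0% to 3.6% | 0.0% to 2.7% |
| 0/15 and 0/15 | 2.5 | 0.04% to 9.0% | 0.03% to 6.8% |
| 0/15 and 0/15 | 1.5 | 0.4% to 13.0% | 0.3% to 10.1% |
| 0/15 and 2/15 | 1000 | 0.7% to 18.8% | 0.8% to 19.8% |

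Pooled totals of 0/10 and 0/50 also give 0% to 0% with SD 1000, so the result does not hinge on stratum size. The last row shows pooling doing its job when one arm has responders.

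**5. Beta(0.5, 0.5) for comparison.** Upper limits are 16.2% for 0/14 (Beta(0.5, 14.5)), 8.5% for 0/28 and 8.0% for 0/30.

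**6. Arm-level rate.** Taken as the sample-size-weighted average of stratum rates, the 0/14 case gives 20.0% (SD 1000) against 20.1% (SD 2.5) in Arm 1, and 14.0% against 14.1% in Arm 2. In the 0/15 case the Arm 1 interval is 10.7% to 31.0% against 10.7% to 30.5%.

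**7. Chance of an empty level.** (1 − p)^n for 20 to 35 participants across both arms (an assumed range) is 67% to 49% at a true SVR of 2%, 36% to 17% at 5%, 12% to 2.5% at 10%, and about 1% or less at 20%.

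**8. Diagnostics.** With a two-chain Metropolis sampler (5,000 burn-in, 10,000 draws per chain) at SD 1000, the BGR was about 1.00 to 1.04 when the γ2 proposal step was wide (50 or 1500). It was 2.37, 1.47 and 1.04 in three runs with step 0.7, and 1.72, 2.41 and 1.72 with step 5.

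**The case against.** The case for leaving the model alone has substance. The SAP names zero-count strata as the source of the separation, and the version history claims only to cure what happens when arms are fitted separately, which pooling does. No document reports a level empty in both arms. SAP Table 8 projects primary-endpoint data on 100 participants by January 2023, and v4.0 is dated March 2023, so the team may have had no such level in view. SAP 4.6.1 prints the number of responders next to each interval, allows descriptive summaries for categories below five participants, and makes no comparison between subgroups. These points make the error conditional and visible to a careful reader. They do not make a 0% to 0% interval right where it occurs.

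Some stronger readings are tempting, and the documents do not support them.

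- A reader might infer that the wide priors cause the separation. The zero counts do; the priors fail to contain it.
- A reader might infer that the primary result is distorted. The weighted-average arm-level rate moves by about 0.1 percentage points.
- A reader might infer that the convergence checks would pass the output unnoticed. Step 8 shows that this depends on sampler tuning, which the SAP does not specify. The gap is that no action follows a failed check.
- A reader might infer that these stratum rates choose the Phase III population. SAP 2 speaks of selecting a treatment regimen from the comparison between arms.
- A reader might see a contradiction with the Beta(0.5, 0.5) design model. SAP 5 says its operating characteristics ignore the stratification factors, so the two models differ by intent.

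**Conclusion.** The analysis as written gives a wrong stratum and subgroup output whenever a stratification-factor level has no responders in either arm: an interval of essentially 0% to 0%, where reasonable alternatives give upper limits of roughly 7% to 16% for 0/14 per arm. Whether this arises cannot be told from the documents. It is plausible if the true SVR at a level is around 5% or lower, and unlikely at 10% or more with 35 participants.

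The size of the correction rests on assumed stratum data and on the replacement prior. The collapse itself rests on neither. The finding that the arm-level rate is stable assumes the weighted-average reading of the SAP 4.2.2 formula. Read as a literal mixture of densities, the Arm 1 interval in the 0/15 case would run from about 0% to 54%. Even with the SD 2.5 prior it would be 0.1% to 51%, so that is a separate question from the priors. This is a point to correct before the subgroup tables are produced; it does not threaten the primary estimate.

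**What to change.** In SAP 4.2.2, replace Normal(0, 10^6) with a pre-specified weakly informative prior on τ, γ1, γ2 and γ3, for example Normal with mean 0 and SD 2.5 on the log-odds scale. This also supplies the missing prior for the arm effect. Add a short prior-sensitivity table (for example SD 1.5, 2.5 and 10). For any stratum or factor level with no responders, report the Beta(0.5, 0.5) interval beside the model-based one.

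The cost is a few lines of SAP text, a changed prior statement in the program and one extra table. The statistical price is mild shrinkage of the stratum effects. The upper limit for an empty level will depend somewhat on the chosen SD (about 4% to 13% for Arm 1 in the 0/30 pooled case as SD goes from 10 to 1.5), and the sensitivity table makes that visible.
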